### 10 ADVERSE EVENTS

### **10.1 Adverse Event**

An AE is defined as any untoward medical occurrence associated with the use of an IP in humans, whether or not considered IP-related. An AE can be any unfavorable and unintended sign (e.g., an abnormal laboratory finding), symptom, or disease temporally associated with the use of an IP, without any judgment about causality. An AE can arise from any use of the IP (e.g., off-label use, use in combination with another drug or medical device) and from any route of administration, formulation, or dose, including an overdose. An AE can arise from any delivery, implantation, or use of a medical device, including medical device failure, subject characteristics that may impact medical device performance (e.g., anatomical limitations), and therapeutic parameters (e.g., energy applied, sizing, dose release, and anatomic fit) associated with medical device use.

All AEs spontaneously reported by the subject and/or in response to an open question from study personnel or revealed by observation, physical examination or other diagnostic procedures will be recorded in the source document and on the appropriate pages of the CRF. Any clinically relevant deterioration in clinical finding is considered

an AE and must be recorded. When possible, signs and symptoms indicating a common underlying pathology should be noted as one comprehensive event.

Documentation regarding the AE should be made as to the nature, date of onset, end date, severity, and relationship to IP, action(s) taken, seriousness, and outcome of any sign or symptom observed by the physician or reported by the subject upon indirect questioning. Exacerbation of conditions related to the signs and symptoms of Dry Eye will not be reported as an AE.

#### 10.1.1 Severity

Severity of an AE is defined as a qualitative assessment of the degree of intensity of an AE as determined by the investigator or reported to him/her by the subject. The assessment of severity is made irrespective of relationship to IP or seriousness of the event and should be evaluated according to the following scale:

#### 10.1.2 Relationship to Investigational Product

The Investigator must assess whether they consider an AE to be drug-related. In assessing this relationship, the Investigator must use information about the conditions/concurrent medication, and chronology of the event relative to drug administration. The following definitions will be used:

- Definitely Related
- Probably Related
- Possibly Related
- Unlikely to be related
- Not Related

#### 10.1.3 Expectedness

The expectedness of an AE should be determined based upon existing safety information about the IP using these explanations:

- *Unexpected:* An AE that is not listed in the Investigator's Brochure (IB) or is not listed at the specificity or severity that has been observed.
- *Expected:* An AE that is listed in the IB at the specificity and severity that has been observed.
- *Not applicable:* An AE unrelated to the IP.

AE events that are mentioned in the IB as occurring with a class of products or as anticipated from the pharmacological/mechanical (or other) properties of the product, but are not specifically mentioned as occurring with the particular product under investigation are to be considered unexpected.

The investigator should initially classify the expectedness of an AE, but the final classification is subject to the Medical Monitor's determination.

#### 10.2 Serious Adverse Events

An AE is considered serious if, in the view of either the investigator or sponsor, it results in any of the following outcomes:

- Death;
- A life-threatening AE;

Note: An AE is considered "life-threatening" if, in the view of either the investigator or sponsor, its occurrence places the subject at immediate risk of death. It does not include an AE that, had it occurred in a more severe form, might have caused death.

Inpatient hospitalization or prolongation of existing hospitalization;

Note: The term "inpatient hospitalization" refers to any inpatient admission (even if less than 24 hours). For chronic or long-term inpatients, inpatient admission includes transfer within the hospital to an acute/intensive care inpatient unit. Inpatient hospitalization does not include: emergency room visits; outpatient/same-day/ambulatory procedures; observation/short stay units; rehabilitation facilities; hospice facilities; nursing homes; or clinical research/phase 1 units.

Note: The term "prolongation of existing hospitalization" refers to any extension of an inpatient hospitalization beyond the stay anticipated or required for the reason for the initial admission as determined by the investigator or treating physician.

 A persistent or significant incapacity or substantial disruption of the ability to conduct normal life functions;

Note: A serious adverse event (SAE) specifically related to visual threat would be interpreted as any potential impairment or damage to the subject's eyes (e.g., hemorrhage, retinal detachment, central corneal ulcer or damage to the optic nerve).

• A congenital anomaly/birth defect.

Important medical events that may not result in death, are life-threatening, or require hospitalization may be considered serious when, based upon appropriate medical judgment, they may jeopardize the subject and may require medical or surgical intervention to prevent one of the outcomes listed in this definition.

#### **10.3 Procedures for Reporting Adverse Events**

All AEs and their outcomes must be reported to Ora, the sponsor, and the IRB/IEC as required by the IRB/IEC, federal, state, or local regulations and governing health

authorities and recorded on the appropriate CRF. Adverse Events will be collected after the signing of the Informed Consent.

#### 10.3.1 Reporting a Suspected Unexpected Adverse Reaction

[figure not shown]
All AEs that are 'suspected' and 'unexpected' are to be reported to Ora, the sponsor and the IRB/IEC as required by the IRB/IEC, federal, state, or local regulations and governing health authorities.

#### 10.3.2 Reporting a Serious Adverse Event

To ensure subject safety, all SAEs, regardless of relationship to the IP, must be immediately reported. All information relevant to the SAE must be recorded on the appropriate CRFs. The investigator is obligated to pursue and obtain information requested by Ora and/or the sponsor in addition to that information reported on the CRF. All subjects experiencing a SAE must be followed up and the outcome reported.

In the event of a SAE, the investigator must notify Ora and the sponsor immediately; obtain and maintain in his/her files all pertinent medical records, information, and medical judgments from colleagues who assisted in the treatment and follow-up of the subject; provide Ora and the sponsor with a complete case history, which includes a statement as to whether the event was or was not suspected to be related to the use of the IP; and inform the IRB of the SAE within their guidelines for reporting SAEs.

Contact information for reporting SAEs:

### 10.4 Procedures for Unmasking (if applicable)

All subjects, investigators, and study personnel involved with the conduct of the study will be masked with regard to treatment assignments. When medically necessary, the investigator may need to determine what treatment group has been assigned to a subject. When possible (i.e., in non-emergent situations), Ora and/or the study sponsor should be

notified before unmasking study drug. Ora and/or the study sponsor must be informed immediately about any unmasking event.

If an investigator identifies a medical need for unmasking the treatment assignment of a subject, he/she should contact Ora and/or the medical monitor prior to unmasking the identity of the IP, if possible. Ora will ask the site to complete and send them the Unmasking Request Form. Ora will notify Aldeyra and jointly will determine if the unmasking request should be granted. They may consult the medical monitor as needed. The result of the request will be documented on the Unmasking Request Form. If approval is granted to unmask a subject, written permission via the Unmasking Request Form will be provided to the investigator. The investigator will unmask the subject using IWRS. The investigator will complete the Unmasking Memo form and include it in the subject's study file and provide a copy for the TMF. For each unmasked request, the reason, date, signature, and name of the person who unmasked the subject, must be noted in the subject's study file.

Unmasked subjects will be discontinued from the study.

# 10.5 Type and Duration of the Follow-up of Subjects after Adverse Events

The investigator will follow unresolved AEs to resolution until the subject is lost to follow-up or until the AE is otherwise classified. Resolution means the subject has returned to baseline state of health or the investigator does not expect any further improvement or worsening of the AE. If the subject is lost to follow-up, the investigator should make 3 reasonable attempts to contact the subject via telephone, post, or certified mail. All follow-up will be documented in the subject's source document. Non-serious AEs identified on the last scheduled contact must be recorded on the AE eCRF with the status noted.

If the investigator becomes aware of any new information regarding an existing SAE (i.e., resolution, change in condition, or new treatment), a new SAE/Unanticipated Report Form must be completed and faxed to Ora within 24 hours of the site's awareness of the new information. The original SAE form is not to be altered. The report should describe whether the event has resolved or continues and how the event was treated.

#### 11 STATISTICAL HYPOTHESES AND METHODS OF ANALYSES

[figure not shown]
#### 11.1 Analysis Populations

The following analysis populations will be considered:

• Intent-to-Treat Population – The intent-to-treat (ITT) population includes all randomized subjects. Subjects in the ITT population will be analyzed as randomized.

- Per-Protocol Population The per-protocol (PP) population includes subjects in the ITT population who do not have significant protocol deviations and who complete the study. Protocol deviations will be assessed prior to database lock and unmasking. Subjects in the PP population will be analyzed as treated.
- Safety Population The safety population includes all randomized subjects
  who have received at least one dose of the investigational product. Subjects in
  the Safety population will be analyzed as treated.

The statistical analysis of safety data will be performed for the safety population. The analysis of efficacy data will be performed for the ITT population and on the PP population as sensitivity analyses.

Aldeyra Therapeutics, Inc.

#### 11.4.1 General Considerations

Quantitative variables will be summarized descriptively using number of subjects (n), mean, standard deviation, median, minimum, and maximum. Qualitative variables will be summarized using counts and percentages.

All summaries will be presented by treatment group. Summaries will be provided for demographics, baseline medical history, concurrent therapies, and subject disposition.

For the purpose of summarization, medical history, concurrent therapies, and adverse events will be coded to MedDRA and WHO Drug dictionaries, as appropriate.

All analyses will be 2-sided at a significance level of 0.05. 80% and 95% confidence intervals will be provided where appropriate.

#### 11.4.2 Unit of Analysis

Safety endpoints will be analyzed for both eyes. For efficacy endpoints, the unit of analysis will be the study eye, or the "worst eye," as defined by the following:

Analyses will be performed on the ITT population with the Last Observation Carried Forward (LOCF) imputation method for missing values. Efficacy analyses may also be conducted using the ITT population with observed data only (i.e., without LOCF) and the PP population to assess sensitivity as detailed further in the statistical analysis plan (SAP).

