### 3 STUDY OBJECTIVES

The study objectives are as stated below:

- To evaluate the efficacy of Reproxalap Ophthalmic Solutions (0.25% and 0.1%) on baseline to weeks 2, 4, 8 and 12 change scores
- To evaluate effect sizes for efficacy endpoints of Reproxalap Ophthalmic Solutions (0.25% and 0.1%) versus vehicle for the treatment of the signs and symptoms of dry eye disease to confirm the endpoint selection and sample size for Phase 3 studies with ADX-102.
- To evaluate the safety and tolerability of Reproxalap Ophthalmic Solutions (0.25% and 0.1%) to vehicle

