### 5 OVERALL STUDY DESIGN

This is a Phase 2b, multicenter, randomized, double—masked, vehicle-controlled, parallel-group design with block enrollment. Subjects will be randomized to one of the following treatment groups at Visit 2 and will be instructed to follow a QID-dosing regimen:

[figure not shown]
- Reproxalap 0.1% Ophthalmic Solution (N~100)
- Reproxalap 0.25% Ophthalmic Solution (N~100)
- Vehicle of Reproxalap Ophthalmic Solution (N~100)

[figure not shown]
This study is multicenter, randomized, double—masked, vehicle—controlled, parallel-group design with block enrollment. Approximately 300 subjects will be randomly assigned to one of the three treatment groups (1:1:1) to receive either Reproxalap Ophthalmic Solution (0.1%, 0.25%) or vehicle solution as topical ophthalmic drops administered bilaterally QID. Subjects, Sponsor, CRO and site personnel will be masked to treatment assignment.

During the screening period, two 90-minute exposures to the CAE® will be conducted to ascertain eligibility to enter the study. Those who qualify will be randomized to receive study drug in a double-masked fashion for 84 days. Subjects will self-administer drops four times daily and will complete daily diary assessments as instructed.

At Visit 6 (Day 85), CAE® exposure will occur, with pre-CAE®, during CAE® (symptoms only) and post-CAE® assessments of ocular signs and symptoms. At Visits 3, 4 and 5, no CAE® exposure will occur

The total number of expected participants, including screen failures, is approximately 750 subjects.

Subjects who terminate early during the treatment period will be asked to complete safety assessments prior to commencement of any alternative dry eye therapy (if at all possible). Subjects who are terminated early from the study will not be replaced.

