### 7 STUDY PARAMETERS

### 7.1 Efficacy Measures and Endpoints

### 7.1.1 Efficacy Measure(s)

### 7.1.2 Efficacy Endpoint(s)

The efficacy endpoints are changes from baseline at weeks 2, 4, 8 and 12 for each efficacy measure, where available. Endpoints will be calculated pre-CAE and, where available post-CAE and as pre- to post-CAE changes.

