### 7.1.3 Criteria for Effectiveness

Success would be demonstrating statistically significant (p<0.05) effects on at least one DED sign or at least one DED symptom at week 12

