This SAP describes the data that will be analyzed and the subject characteristics, efficacy, and safety assessments that will be evaluated. This SAP provides details of the specific statistical methods that will be used. The statistical analysis methods presented in this document will supersede the statistical analysis methods described in the clinical protocol. In keeping with the preliminary nature of a Phase 2 study, additional analyses other than the planned analyses described herein may be conducted as adhoc analyses and will be identified in the CSR. The intent of any such analyses would be to better characterize treatment effects and improve the design of a future Phase 3 study.

2. Study Objectives

The study objectives are as stated below:

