2.1 Study Variables

In this Phase 2b study there are no primary or secondary endpoints. All endpoints are considered hypothesis-generating and not hypothesis-testing. Efficacy variables and safety variables follow.

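### The protocol names LOCF as the efficacy analysis and the SAP's output lists keep it, so an earlier value can stand for week 12 in a trial meant to inform Phase 3 sizing

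*Protocol*

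**What the plan says.** The governing sentence is printed under Protocol 11.4.2 Unit of Analysis; the contents list a separate 11.4.3 Missing Data, whose heading is not readable. It reads: "Analyses will be performed on the ITT population with the Last Observation Carried Forward (LOCF) imputation method for missing values". It goes on: "Efficacy analyses may also be conducted using the ITT population with observed data only (i.e., without LOCF) and the PP population to assess sensitivity". Protocol 11.1 is firmer on the second part and commits to a per-protocol (PP) sensitivity analysis of efficacy.

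On endpoints, Protocol 7.1.2 says: "The efficacy endpoints are changes from baseline at weeks 2, 4, 8 and 12 for each efficacy measure, where available". Protocol 7.1.3 sets the test of success: "Success would be demonstrating statistically significant (p<0.05) effects on at least one DED sign or at least one DED symptom at week 12". Under Protocol 3, effect sizes are to be evaluated "to confirm the endpoint selection and sample size for Phase 3 studies with ADX-102".

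SAP 1 says: "The statistical analysis methods presented in this document will supersede the statistical analysis methods described in the clinical protocol". The sections that would state the SAP's own rule (8.2, 13, 16 and 17) are not readable in the public copy, nor is the content of Protocol 11.4.5. The output lists are readable. SAP 20 lists 46 efficacy tables on ITT with LOCF and 93 on observed data only, with LOCF first for each continuous measure. SAP 22 lists four figures, all on LOCF. SAP 2.1 adds: "All endpoints are considered hypothesis-generating and not hypothesis-testing".

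**The concern.** For a subject who leaves early, LOCF enters a week-2, week-4 or week-8 value as the week-12 value. If the treatment effect is still growing, those values understate what week 12 would have shown. With equal dropout, the estimated difference shrinks. With unequal dropout, it can move either way, because the arm that loses more subjects has its change from baseline pulled further towards zero.

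This trial names no primary endpoint and its endpoints are exploratory, so the size of the estimate matters more than the p-value. A biased week-12 effect size would pass into the choice of Phase 3 endpoints and the Phase 3 sample size. No readable text says which of the several estimates will be used for that.

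**Working it through.** **Table count (SAP 20).**
- LOCF: 14.2.1 (8), 14.2.5 (8), 14.2.10, .14, .18 and .22 (4), 14.2.26 (5), 14.2.28 (6), 14.2.30 (13), 14.2.34 and .38 (2). Sum 46.
- Observed data: 14.2.2-.4 (24), .6-.8 (24), .9 (1), .11-.13, .15-.17, .19-.21 and .23-.25 (12), .27 (5), .29 (6), .31 (13), .32-.33 (2), .35-.37 and .39-.41 (6). Sum 93.

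**Inputs.** From the documents: 100 per arm, 1:1:1, two-sided 0.05, visits at weeks 2, 4, 8 and 12. No dropout rate, SD, effect size or time course is readable, so there is no figure of the plan's to reproduce and the rest is illustration. Assumed: SD 1; true week-12 difference -0.30 had all subjects completed (negative is improvement); vehicle change between -0.25 and -1.0; each arm reaching 40/60/80/100% of its change at weeks 2/4/8/12; last visits of dropouts spread evenly over weeks 2, 4 and 8. Dropout is written vehicle/active.

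**Case 1: dropout unrelated to outcome.** The mean carried fraction is (0.4 + 0.6 + 0.8)/3 = 0.6, and its mean square is (0.16 + 0.36 + 0.64)/3 = 0.3867. For an arm with mean change μ and dropout d:

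- LOCF mean = μ(1 - 0.4d)
- LOCF variance = 1 + μ²[(1 - d) + 0.3867d - (1 - 0.4d)²]
- Phase 3 n per arm at 80% power = 15.698 × mean variance / difference², where 15.698 = 2(1.95996 + 0.84162)²

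Without bias, n = 15.698/0.09 = 174.4, rounded up to 175.

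At 10%/10% the difference is -0.30 × 0.96 = -0.288. With vehicle change -0.25, the bracket is 0.9 + 0.03867 - 0.9216 = 0.01707, the mean of 0.25² and 0.55² is 0.1825, the mean variance is 1.0031, and n = 15.698 × 1.0031/0.082944 = 189.8. At 5%/15% the difference is -0.55 × 0.94 + 0.25 × 0.98 = -0.272 (vehicle change -0.25) or -1.3 × 0.94 + 1.0 × 0.98 = -0.242 (vehicle change -1.0).

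| Dropout | LOCF estimate (vehicle change -0.25 to -1.0) | Phase 3 n per arm, unrounded |
|---|---|---|
| 10%/10% | -0.288 | 189.8 to 193.6 |
| 8%/12% | -0.282 to -0.270 | 198.6 to 221.1 |
| 5%/15% | -0.272 to -0.242 | 213.0 to 274.8 |
| 15%/5% | -0.304 to -0.334 | 170.2 to 143.5 |

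**Against precision.** The standard error of a difference is √(2/100) = 0.141. The shift at 10%/10% is 0.012, or 0.012/0.141 = 0.085 standard errors. At 5%/15% it is 0.028 to 0.058, or 0.20 to 0.41 standard errors.

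**Other time courses.** If 80/100/100% of the change is present at weeks 2/4/8, LOCF gives -0.298 at 10%/10% and -0.295 to -0.290 at 5%/15%. With a slower 20/40/70%, it gives -0.283 and -0.260 to -0.218.

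**Cases 2 and 3: dropout related to outcome.** These are simulations with correlation 0.6 between visits and logit slope 1, less improvement making dropout more likely. Case 2 (3,000 runs) depends on the last observed change; Case 3 (2,500 runs) depends on the unseen week-12 value. Each cell gives vehicle change -0.25, then -1.0.

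| Case, dropout | LOCF | Observed data | Mixed model |
|---|---|---|---|
| 2, 8%/12% | -0.267, -0.258 | -0.324, -0.323 | -0.301, -0.302 |
| 2, 5%/15% | -0.236, -0.203 | -0.358, -0.355 | -0.300, -0.298 |
| 2, 15%/5% | -0.338, -0.367 | -0.242, -0.240 | -0.300, -0.296 |
| 3, 8%/12% | -0.291, -0.279 | -0.336, -0.336 | -0.321, -0.321 |
| 3, 5%/15% | -0.302, -0.266 | -0.393, -0.390 | -0.355, -0.352 |
| 3, 15%/5% | -0.273, -0.308 | -0.204, -0.209 | -0.242, -0.247 |

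A separate large-sample calculation agreed to within about 0.01. In Case 2, LOCF and observed data err in opposite directions and the mixed model stays near -0.30. In Case 3, at unequal dropout, the mixed model is biased too and no better than LOCF, whose two biases partly offset.

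**The case against.** The strongest reply is that the quoted sentence is protocol text, that SAP methods override it, and that the SAP sections which would name the lead analysis cannot be read. This stands as a limit. A reader might infer from the table order and the figures that the SAP makes LOCF primary, or that Phase 3 will be sized from it. The documents do not support either: order is not a statement of primacy, observed-data tables outnumber LOCF tables 93 to 46, and their titles are cut, so some may already be model-based. What survives is narrower. The protocol states the rule, and the readable SAP lists have not dropped it.

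Second, alternatives are planned. The protocol's optional observed-data analyses became listed output in the SAP, and Protocol 11.1 commits to PP. That is right, and results will stand side by side. But PP requires study completion, and a week-12 observed-data comparison also rests on those still present. Neither resolves outcome-related dropout.

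Third, the bias is small beside the noise. Around -0.30 the 95% interval is ±1.96 × 0.141, or about -0.58 to -0.02. In Case 1 with no true effect, rejection at 8%/12% is 5.0 to 5.1%. The large shifts need a threefold dropout imbalance that nothing in the documents predicts. This stands and limits the weight of the point.

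Fourth, the mixed model is no cure. In Case 3 at 5%/15%, its -0.352 to -0.355 implies 15.698/0.352² = 126.7 down to 15.698/0.355² = 124.6 per arm, an undersized Phase 3. This stands too, and is why the other analyses should be kept.

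**Conclusion.** The point holds in a limited form. LOCF is the protocol's stated efficacy analysis and remains in the SAP's tables and all four figures. For measures with earlier post-baseline visits, it reports earlier values as week 12 in a trial whose effect sizes are to inform Phase 3.

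Under the assumptions above, the cost at equal 10% dropout is slight: 0.012 on an effect of 0.30, and 190 to 194 per arm instead of 175. It grows, in either direction, with unequal dropout, and is negligible if onset is nearly complete by week 2. If dropout follows observed response, a mixed model is close to unbiased while LOCF and observed data disagree. If it follows unseen values, the mixed model is biased as well. All sizes rest on assumed inputs.

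A reader might also infer, from "At Visits 3, 4 and 5, no CAE® exposure will occur", that pre-treatment values will be carried to week 12 for post-CAE endpoints. The documents do not say so. The missing-data text in SAP 8.2 and the content of any early-termination visit are not readable, and Protocol 7.1.2 limits endpoints to measures that are available. No such claim is made here.

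**What to change.** Unless the unreadable SAP text already does so:

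1. In SAP 8.2 and 13, for measures with more than one post-baseline visit, lead with a mixed model for repeated measures on observed data: baseline, treatment, visit and treatment-by-visit, with unstructured covariance, and the week-12 contrast of each dose with vehicle. State that it estimates the difference had all subjects stayed in the study.
2. Name that contrast as the source of Phase 3 effect sizes, and base the four figures in SAP 22 on it.
3. Keep the listed LOCF and observed-data tables as sensitivity analyses, and add a delta-adjusted check of missing-at-random for endpoints taken to Phase 3.

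The cost is SAP wording and some extra programming before unmasking, with no new data or visits. The downside is reliance on missing-at-random, which fails when dropout depends on unseen values; the retained and added analyses are there to expose that.
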